**Table 6-3 Permitted medication if dose is stable for at least 1 month prior to randomization**

Medication

• Oral anti-diabetic medications such as metformin, sulfonylureas (including glyburide (glibenclamide), meglitinides (such as repaglinide) and thiazolidinediones (including pioglitazone and rosiglitazone)

• Insulin (within 25% of the dose at randomization)

• Beta-blockers and thiazide diuretics. Thiazide diuretic use should also be maintained constant throughout the trial, if possible.

• Fibrates, statins niacin, ezetimibe

• Vitamin E

• Thyroid hormone

• Psychotropic medications (phenothiazines or second generation antipsychotics)

• Hormonal (estrogen, progesterone, or estrogen/progesterone containing) birth control

There is a potential for nidufexor to increase exposure of drugs metabolized by CYP2C8 (including repaglinide, pioglitazone and rosiglitazone) and those dependent on export by BCRP (potentially glyburide (glibenclamide), atorvastatin, rosuvastatin and pitavastatin). Careful attention MUST be paid to the drug interaction sections of the prescribing information for these compounds

Unless adjustment is required due to intercurrent illness;

Unless adjustment is required to treat medically significant increases in LDL-C that have been confirmed upon repeat testing.

### 6.2.3 Restriction for study patients

For the duration of the study, the patients should be informed and reminded of the restrictions outlined in this section. See also male and female contraception requirements in [Section 5.2](#)

In the event a patient presents with symptoms of COVID-19, the Investigator should ask the patient to quarantine per local guidelines.

#### 6.2.3.1 Dietary restrictions and smoking

No special restrictions for the study. Appropriate diet for type 2 diabetes should be followed.

#### 6.2.3.2 Other restrictions

None.

## **6.3 Patient numbering, treatment assignment, randomization**

### **6.3.1 Patient numbering**

The patient number assigned to a patient at screening remains the unique identifier for the patient throughout the study. For information on patient numbering, please see ‘patient numbering’ section in the Site Operations Manual.

### **6.3.2 Treatment assignment, randomization**

Randomized treatment will be assigned by the IRT to individual patients by way of a randomization number. Randomization numbers will be assigned in ascending, sequential order to eligible patients (see Site Operations Manual for details). However, randomization numbers will not be shared with the study staff, and will remain on the back-end of the IRT system.

The randomization number is only used to identify which treatment the patient has been randomized to receive. The patient number assigned to a patient at screening remains the unique identifier for the patient throughout the study.

The randomization numbers will be generated using the following procedure to ensure that the treatment assignment is unbiased and concealed from patients and investigator staff:

- A patient randomization list will be produced by the IRT provider using a validated system that automates the random assignment of treatment arms to randomization numbers.
  - *Note: These randomization numbers are linked to the different treatment arms.*
- The randomization scheme for patients will be reviewed and approved by a member of the Randomization Office. If a patient is deemed eligible for enrollment into the study, they will be randomized and treatment will be assigned via the IRT system.
- Patients will be assigned randomization numbers 5101-5340.
  - *Note: Follow the details outlined in the Site Operations Manual regarding the process and timing of treatment assignment and randomization of patients.*

## **6.4 Treatment blinding**

This is a patient- and investigator-blinded study. Patients, investigators, and sponsor staff (see [Table 6-4](#)) will remain blinded to study treatment throughout the study, except where indicated below.

The identity of the treatments will be concealed by the use of study drugs that are all identical in packaging, labeling, schedule of administration, appearance, and odor.

### **6.4.1 Treatment blinding - study staff**

All study staff (including study investigator, study nurses/coordinators) will be blinded to study treatment throughout the study. Unblinding a single patient for safety reasons (i.e. necessary for patient safety management) will occur via an emergency system (see SOM and IRT manual for details).

#### 6.4.2 Treatment blinding - sponsor staff

The following are unblinded sponsor roles:

- Sponsor randomization office
- Drug supply (global clinical supplies)
- Study statistician
  - The study statistician will be able to access the randomization list and is allowed to share unblinded information with the rest of the clinical team as appropriate for internal decision purposes. *For example, unblinded summaries and unblinded individual data can be shared with the team for interim analyses.*

The following are additional unblinded sponsor roles:

- Medical lead (study safety physician / TME) and sponsor pharmacovigilance staff
  - *Note: The TME and pharmacovigilance staff may have access to individual, group/cohort, or the entire study treatment allocations as needed to oversee safety on the trial.*
- Other sponsor roles:
  - The sample analysts will receive a copy of the randomization schedule (via request to the Randomization Office), to facilitate analysis of the PK samples. The sample analysts will provide the sample data to the study team under blinded conditions unless otherwise allowed.
  - Study programmers and other personnel involved in study data analysis (e.g. PK expert, CCI ) are allowed to access treatment assignment information for the purpose of conducting interim analyses of the data.
  - The clinical trial team is allowed to share unblinded results with other sponsor staff (e.g. decision boards) as required for internal decision making on the study or the project at the time of interim analyses while the study is ongoing.
  - All unblinded personnel will otherwise keep randomization lists and data or information that could unblind other study team members confidential and secure except as described above.

**Following final database lock ALL roles are considered unblinded.**

**Table 6-4 Blinding and unblinding plan**

Role	Time or Event			
	Randomization list generated	Treatment allocation & dosing	Safety event (single subject unblinded)	Interim Analysis
Patient	B	B	UI*	B
Site staff, including PI, SC, study nurses and mobile health professionals	B	B	UI*	B
Unblinded Pharmacovigilance sponsor staff	B	UI	UI	UI
All other sponsor staff, including: 
 
• TME
 
• Study Leader
 
• Bio-analysts, including PK and BMD
 
• Bio-experts, including PK and BMD
 
• Statistical programmers
 
• Data analysts
 
• Clinical trial team members
 
• Sponsor management and decision boards
 
• Supportive functions
 
	B	UI	UI	UI
Drug Supply (Global Clinical Supplies)	UI	UI	UI	UI
Sponsor Randomization Office	UI	UI	UI	UI
Study Statistician	UI	UI	UI	UI

Key:

*\*Unblinding allowed at the single patient level ONLY*

**UI:** Allowed to be unblinded on individual patient level (includes single patient, group/cohort of patients, or entire study/all patients)

**B:** Remains blinded

## 6.5 Dose escalation and dose modification

Investigational or other study treatment dose adjustments and/or interruptions should be kept as short as possible and dates recorded in the eCRF. If these are for reasons of significant noncompliance or extended dosing interruptions related to AEs, the investigator should use discretion to discontinue the patient from study treatment. The investigator may consult with the Sponsor medical lead if necessary.

If this modification is not tolerated, the medication should be discontinued. Please refer to [Section 9.1.1](#).

If the reduced dose is tolerated, an attempt to increase the dose after two weeks of reduced dosing could be considered or the reduced dose can continue for the remainder of the study. Use of bile acid binding resins for treatment of pruritus is not recommended.

The ability to reduce the dose is clinically relevant as data generated after dose reduction will provide further information regarding the tolerability and safety of nidufexor.

In the event a patient develops flu-like symptoms during the treatment period and the investigator is concerned the patient may have a COVID-19 infection, treatment interruption may be considered. If an investigator decides to interrupt study treatment for this reason, the investigator must ensure that the patient has a SARS-Cov-2 PCR test to confirm the infection within approximately 5 days.

- If the test is positive, the investigator may decide to extend the treatment interruption and monitor the patient's condition to determine if discontinuation is warranted. Treatment interruption should not exceed 14 days.
- If the test is negative, the investigator may decide to resume study treatment.

## **6.6 Additional treatment guidance**

### **6.6.1 Treatment compliance**

The investigator must promote compliance by instructing the patient to take the study treatment exactly as prescribed, and by stating that compliance is necessary for the patient's safety and the validity of the study. The patient must also be instructed to contact the investigator if he/she is unable for any reason to take the study treatment as prescribed.

Compliance will be assessed by the Investigator and/or study personnel (or delegate) at each visit using pill counts and information provided by the patient. This information should be captured in the source document at each visit. All study treatment dispensed and returned must be recorded in the Drug Accountability Log. Patients who are not >80% compliant with study drug administration will be counseled by the investigator and reminded by site personnel or delegate regarding the importance of taking all doses. Dose reductions due to tolerability issues should not be factored into the compliance calculation.

### **6.6.2 Recommended treatment of adverse events**

At present there is insufficient information to provide specific recommendations regarding treatment of adverse events.

Medication used to treat AEs must be recorded on the Concomitant Medications/Significant non-drug therapies CRF.

### **6.6.3 Emergency breaking of assigned treatment code**

Emergency code breaks must only be undertaken when it is required in order to treat the patient safely. Blinding codes may also be broken after a participant discontinues treatment due to disease progression if deemed essential to allow the investigator to select the participant's next treatment regimen, and after discussion and agreement with the sponsor. Most often, study treatment discontinuation and knowledge of the possible treatment assignments are sufficient to treat a study patient who presents with an emergency condition.

Emergency treatment code breaks are performed using the IRT. When the investigator contacts the system to break a treatment code for a patient, he/she must provide the requested patient identifying information and confirm the necessity to break the treatment code for the patient. The investigator will then receive details of the investigational drug treatment for the specified patient and a fax or email confirming this information. The system will automatically inform the Novartis monitor for the site and the study team that the code has been broken.

It is the investigator's responsibility to ensure that there is a dependable procedure in place to allow access to the IRT at any time in case of emergency.

The investigator will provide:

- protocol number
- protocol title
- patient number

In addition, oral and written information to the patient must be provided on how to contact his/her backup in cases of emergency, or when he/she is unavailable, to ensure that un-blinding can be performed at any time.

Patients should be discontinued from the study after emergency unblinding but should not be considered withdrawn from the study. Where possible, they should return for end-of-study assessments as described in [Section 9.1.1](#).

## **6.7 Preparation and dispensation**

Each study site will be supplied with study drug in packaging as described under the investigational and control drugs section.

A unique medication number is printed on the study medication label.

Investigator staff will identify the study medication kits to dispense to the patient by contacting the IRT and obtaining the medication number(s).

Nidufexor will be administered to the patient via the oral route. On study visit days, administration will occur in the presence of the study nurse or delegate. At home, the patient will self-administer study medication. See the Site Operations Manual for further details.

## **7 Informed consent procedures**

If applicable, in cases where the patient's representative(s) gives consent (if allowed according to local requirements), the patient must be informed about the study to the extent possible given his/her understanding. If the patient is capable of doing so, he/she must indicate agreement by personally signing and dating the written informed consent document.

Informed consent must be obtained before conducting any study-specific procedures (e.g. all of the procedures described in the protocol). The process of obtaining informed consent must be documented in the patient source documents.

Novartis will provide to investigators, in a separate document, a proposed informed consent form that complies with the ICH GCP guidelines and regulatory requirements and is considered appropriate for this study. Any changes to the proposed consent form suggested by the investigator must be agreed by Novartis before submission to the IRB/IEC.

Information about common side effects already known about the investigational drug can be found in the Investigator's Brochure (IB). This information will be included in the patient informed consent and should be discussed with the patient during the study as needed. Any new information regarding the safety profile of the investigational drug that is identified between IB updates will be communicated as appropriate, for example, via an investigator notification or an aggregate safety finding. New information might require an update to the informed consent and then must be discussed with the patient.

Women of child bearing potential must be informed that taking the study treatment may involve unknown risks to the fetus if pregnancy were to occur during the study and agree that in order to participate in the study they must adhere to the contraception requirements.

Male patients must be informed that if a female partner becomes pregnant while he is enrolled in the study, contact with the female partner will be attempted to request her consent to collect pregnancy outcome information.

Commercially Confidential Information

Refer to the Site Operations Manual for a complete list of ICFs included in this study.

## 8 Visit schedule and assessments

The assessment schedule lists all of the assessments and indicates with an “X”, the visits when they are performed. All data obtained from these assessments must be supported in the patient’s source documentation. Some assessments in the schedule are marked with an "S" indicating that these data are to be evaluated and stored as source data at the site.

Patients should be seen for all visits/assessments as outlined in the assessment schedule or as close to the designated day/time as possible. Missed or rescheduled visits should not lead to automatic discontinuation. This also applies in the event a patient needs to be quarantined for an amount of time consistent with local policy due to exposure to or suspected or confirmed COVID-19 infection.

For patients who withdraw from the study (i.e. withdrawal of consent), no further assessments will be conducted. Further attempts to contact the patient are not allowed, unless safety findings require communicating or follow up.

All study assessments described in [Table 8-1](#) may potentially be performed remotely. Implementation of decentralized trial models is dependent on local regulations and Sponsor approval.

**Table 8-1 Assessment Schedule**

Visit Name/Epoch	Screening	Treatment															EOS	Post Study Safety Contact
		101					102					103 	104 	105 	106 	107 		
Visit Numbers 	1	101					102					103 	104 	105 	106 	107 	199	
Days	-30 to -1	1					14 ±5					29 ±5	57 ±5	85 ±5	113 ±5	141 ±5	169 ±5	197 ±5
Time (post-dose)	-	0h 	1h	2h	4h	6h	0h 	1h	2h	4h	6h	-	-	-	-	-	-	-
Informed consent	X																	
Commercially Confidential Information																		
Inclusion / exclusion criteria	X																	
Medical history/current medical conditions	X																	
Demography	X																	
Body height	X																	
Body weight	X	X					X					X	X	X	X	X	X 	

- X Assessment to be recorded in the clinical database  
S Assessment to be recorded in the source documentation only  
1 Visit structure given for internal programming purpose only  
2 Assessments must be performed pre-dose  
3

### Commercially Confidential Information

- 4 Priority in the event of early discontinuation or withdrawal  
5 Waist and hip circumferences (measured in cm); see the SOM for detailed explanation  
6 ECG as triplicate measures  
7 A serum pregnancy test will be performed at screening; a urine pregnancy test will be used at end of study.  
8 Prothrombin Time/International Normalized Ratio  
9 Intentionally deleted in Protocol Amendment V03  
10 PK samples will be collected after patients have been fasting for at least 6 hours

### Commercially Confidential Information

- 11  
12 Dipstick measurements/macroanalysis for specific gravity, protein, glucose and blood will be performed. Microscopy, WBC, RBC and sediments will also be assessed in case of an abnormal dipstick test.  
13 Urine creatinine is collected in parallel with urine albumin and urine protein for the calculation of urine albumin-to-creatinine ratio (UACR). *Note: The sample should be obtained from the 24-hour urine sample at time points when 24-hour collection is required. For visits that are not preceded by a 24-hour collection or due to a premature discontinuation, a separate spot urine sample will be collected and processed during the visit. A second morning void is preferred. If sample quantity is sufficient, then the same 2nd morning void may be used for other urine related assessments.*  
14 Intentionally deleted in Protocol Amendment V03  
15 At time points when 24-hour collection is done prior to a visit, a separate spot urine sample will be collected and processed promptly. A second (2nd) morning void is preferred. If sample quantity is sufficient, then the same 2nd morning void may be used for other urine related assessments.

### Commercially Confidential Information

- 16 24-hour urine collection should be performed as an outpatient, within 1-2 days prior to the study visit, and brought to the study visit, using supplied collection kit + instructions, as applicable. Quantify the urine volume and measure sodium, creatinine, protein, osmolality, and albumin (assays).  
17 PRO: VAS assessment for itching of the skin  
18 On study visit days, study drug should not be taken until after study visit assessments are completed  
19 Collect unused study drug, perform drug accountability (pill count) and document compliance with protocol instructions  
20 A thorough review of any concomitant medications (including medication name, dose, unit, frequency, and route) should be performed at every visit.  
21 It is highly recommended that PCR testing for COVID-19 be completed within 1 week prior to first dosing.

## **8.1 Screening**

In general, it is permissible to re-screen a patient if he/she fails the initial screening, if deemed feasible or necessary by the study site investigator. If a subsequent re-screen is required after the first permissible re-screening (i.e. an additional re-screening attempt), the case should be discussed with the Sponsor. Additional re-screenings may be approved on a case-by-case basis. Further information on re-screening is outlined in the Site Operations Manual.

### **8.1.1 Information to be collected on screening failures**

Patients who sign an informed consent but fail to be started on treatment for any reason are considered a screen failure. Information on data collected for screening failures is available in the SOM.

## **8.2 Patient demographics/other baseline characteristics**

Patient demographic and baseline characteristic data will be collected on all enrolled patients. Details on additional data collected are outlined in the Site Operations Manual.

Investigators have the discretion to record abnormal test findings on the medical history CRF, if in their judgment, the test abnormality occurred prior to the informed consent signature.

### **8.2.1 Hepatitis screen**

All patients will be screened for Hepatitis B and C. See the Site Operations Manual for details.

### **8.2.2 Alcohol test, Drug screen**

All patients will be screened for alcohol and substances of abuse. See the Site Operations Manual for details.

## **8.3 Efficacy and Pharmacodynamics**

Efficacy and Pharmacodynamics (PD) of nidufexor will be assessed based on measures including renal function and type 2 diabetes status.

Pharmacodynamic samples will be collected at the time points defined in the [Assessment Schedule](#). Follow the instructions outlined in the Site Operations Manual regarding sample collection, numbering, processing and shipment. In order to better define the PD profile, the timing of the sample collection may be altered based on emergent data. Results will remain blinded to the patient, investigative personnel, and blinded sponsor personnel regarding the associated treatment assignment throughout the study, as applicable. The number of samples/blood draws and total blood volume collected will not exceed those stated in the protocol. The PD samples will be obtained and evaluated in all patients.

### **8.3.1 Renal function assessments, markers of diabetic nephropathy**

The following assessment will profile renal function, which are markers of diabetic nephropathy:

- Urine albumin-creatinine ratio (UACR) at serial time points, as specified in the [Assessment Schedule](#)

- 24-hour urinary collection at baseline and end of study, measured for albumin
- Estimated glomerular filtration rate (eGFR), as determined by the Chronic Kidney Disease Epidemiology Collaboration (CKD-EPI) equation. ([Levey and Stevens 2010](#))
- Free water clearance

### **8.3.2 Type 2 diabetes measures**

The following assessments will be used to measure Type 2 diabetes status:

- HbA1c
- Weight, BMI, waist-to-hip ratio
- Fasting lipid profile to include total cholesterol, HDL cholesterol, LDL cholesterol, triglycerides and Lp(a)

### **8.3.3 Appropriateness of efficacy assessments**

Change in albuminuria (UACR and 24-hour urine albumin excretion) and annualized rate of change in eGFR over the 24-week treatment period are the primary and secondary endpoints, respectively. These two parameters comprise the current gold standard ([Levey et al 2015](#)) for assessing stage and progression of proteinuric chronic kidney diseases such as diabetic nephropathy secondary to Type 2 Diabetes. The efficacy measures for renal function demonstrate the sensitivity and specificity required to serve as the gold standard diagnostic measures in clinical practice. (UACR sensitivity = .85 and specificity =.88; eGFR sensitivity =.91 and specificity =.87). The efficacy measures for type 2 diabetes are recognized by medical professionals, diabetes organizations, and payers as the essential surrogate and diagnostic measures used for patient monitoring to help patients manage the disease, reduce diabetes symptoms and, if well controlled, minimize or ameliorate diabetes related end organ damage.

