## Protocol summary

Protocol number	CLMB763X2202
Full Title	A randomized patient-and-physician blinded, placebo-controlled, 24-week study to assess the safety, tolerability and efficacy of nidufexor in patients with diabetic nephropathy
Brief title	A study of the safety and efficacy of nidufexor in patients with diabetic kidney disease
Sponsor and Clinical Phase	Novartis Phase 2
Investigation type	Drug
Study type	Interventional
Purpose and rationale	Nidufexor is a potent partial agonist of the bile acid receptor Farnesoid X Receptor. In diabetic nephropathy, hyperglycemia, dyslipidemia and oxidative stress induce fibrosis and inflammation, resulting in endothelial and podocyte epithelial injury. Nidufexor addresses fibrosis, oxidative stress, inflammation and cell death, and therefore has the potential to improve the management of diabetic kidney disease when added to the standard of care (angiotensin converting enzyme inhibitor or angiotensin receptor blocker). This non-confirmatory Phase 2 study is designed to determine the safety, tolerability, efficacy, pharmacokinetics and pharmacodynamics of nidufexor in combination with dose of angiotensin converting enzyme inhibitor (ACEI) or angiotensin receptor blocker (ARB) that is the standard of care as judged by the PI or sub-I in patients with type 2 diabetes and nephropathy.
Primary Objective(s)	To compare the effect of nidufexor to placebo on albuminuria in patients with diabetic nephropathy already receiving treatment with an angiotensin converting enzyme inhibitor (ACEI) or angiotensin receptor blocker (ARB) as measured by serial urinary albumin to creatinine ratio and 24 hour urinary albumin at baseline and end of study.  To assess the safety and tolerability of nidufexor, as measured by vital signs, physical examination, laboratory measurements, electrocardiograms, and reports of adverse events
Secondary Objectives	To assess the pharmacokinetic properties of nidufexor at steady state in patients with type 2 diabetes and nephropathy as measured by -plasma concentrations of nidufexor  To determine the effect of nidufexor on renal tubular function as measured by free water clearance by the kidney  To determine the effect of nidufexor on anthropometric assessments (weight, body mass index, and waist-to-hip ratio)  To determine the effect of nidufexor on lipids as measured by a fasting lipid profile

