## 2 Objectives and endpoints

**Table 2-1 Objectives and related endpoints**

Objective(s)	Endpoint(s)
Primary objective(s)	Endpoint(s) for primary objective(s)
To compare the effect of nidufexor to placebo on albuminuria in patients with diabetic nephropathy already receiving treatment with ACEI or ARB	Urine albumin-creatinine ratio (UACR) at serial time points, as specified in the Assessment Schedule 24-hour urinary albumin at baseline and end of study
To assess the safety and tolerability of nidufexor	Safety endpoints including: vital signs physical examination laboratory measurements ECG parameters adverse events
Secondary objective(s)	Endpoint(s) for secondary objective(s)

Objective(s)	Endpoint(s)
To determine the effect of nidufexor on renal filtration function	Estimated glomerular filtration rate (eGFR), as determined by the Chronic Kidney Disease Epidemiology Collaboration (CKD-EPI) equation ( Levey and Stevens 2010 )
To assess the pharmacokinetic properties of nidufexor on day 1 and at steady state in patients with type 2 diabetes and nephropathy	Cmax, Tmax and AUC0-6h.
To determine the effect of nidufexor on renal tubular function	Free water clearance
To determine the effect of nidufexor on anthropometric assessments	Assessments Weight BMI Waist-to-hip (WTH) ratio
To determine the effect of nidufexor on lipids	Fasting lipid profile, including lipoprotein (a) [Lp(a)]

Commercially Confidential Information

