## **4.2 Rationale for dose/regimen and duration of treatment**

Commercially Confidential Information

The CLMB763X2202 study population is expected to have comparable PK to the CLMBX2201 population.

Commercially Confidential Information

The duration of the study is based on (a) the high variability typical of urine albumin measurements, and (b) the high variability and slow rate of change in eGFR; the 24-week treatment period will allow more robust assessment of a potential anti-proteinuric effect (primary endpoint) and potential slowing of eGFR decline (secondary endpoint). Since both of these parameters demonstrate high intra- and inter-patient variability, repeated measures over 24 weeks will provide more robust data to detect potential treatment effects.

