## **12.5 Analysis of secondary endpoints**

### **12.5.1 Efficacy and/or Pharmacodynamic endpoint(s)**

Log-transformed ratio to baseline for eGFR, free water clearance, HbA1c and fasting lipid profiles (total cholesterol, HDL, LDL, triglycerides and Lp(a)) as well as change from baseline in weight, BMI and WTH ratio will be analyzed using the same repeated measures ANCOVA described in [Section 12.4.2](#) with baseline in lieu of log-transformed baseline as a covariate for change from baseline analysis. For parameters with only one post-treatment measurement an ANCOVA with treatment as a classification factor and baseline (or log-transformed baseline if applicable) as a covariate will be employed.

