### **2.2 Analysis sets**

For all analysis sets, patients will be analyzed according to the study treatment received unless indicated otherwise.

The safety analysis set will include all patients who received any study drug.

The PK analysis set will include all patients with at least one available valid (i.e. not flagged for exclusion) PK concentration measurement, who received any study drug and with no protocol deviations that impact PK data.

The PD analysis set will include all patients with available PD data and no protocol deviations with relevant impact on PD data, with data exclusion including but not limited to:

Commercially Confidential Information

2. EOS visit assessments when they were done earlier than day 135.
3. EOS visit assessments when they were done > 10 days from the last dose.

Commercially Confidential Information

Protocol deviation impact, including the impact due to COVID-19, will be documented appropriately and assessed by the Sponsor study team, including the Medical and Study Leads with input from the trial team.

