### **2.5.2.2 Efficacy and/or pharmacodynamic endpoints**

For all efficacy PD analyses, the PD set will be used.

A Mixed Model for Repeated Measures (MMRM) analysis will be performed for log-transformed ratio to baseline UACR measured at each visit. The model will include effects for log-transformed baseline, treatment, visit, treatment by visit interaction and visit by log-transformed baseline interaction. An unstructured variance-covariance matrix will be used to account for correlation among multiple measurements from the same patient and variance heterogeneity.

Similarly an Analysis of Covariance (ANCOVA) with treatment as the classification factor and log-transformed baseline as the covariate will be conducted for log-transformed ratio to baseline 24-hour urine albumin excretion.

Point estimates, the associated confidence intervals as well as the p-values for treatment difference at each visit will be provided within the MMRM/ANCOVA framework. The null hypothesis of no treatment difference in UACR or 24-hour urine albumin excretion will be tested at the one-sided 0.1 significance level. A treatment difference of at least 25% in favor of LMB763 will be considered clinically significant.

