## 3 Change to protocol specified analyses

No changes from protocol specified analysis were made.

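### Does the annualized eGFR rate named in protocol 4.1 and 8.3.3 leave the secondary eGFR endpoint without a defined analysis?

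*Protocol*

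**What the plan says.** The eGFR endpoint is described in two ways.

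**Rationale text.** Protocol 4.1 and 8.3.3 carry the same sentence, which pairs albuminuria with eGFR: "annualized rate of change in eGFR over the 24-week treatment period are the primary and secondary endpoints, respectively". Protocol 4.2, on the length of treatment, speaks of "potential slowing of eGFR decline (secondary endpoint".

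**Endpoint and analysis text.**
- Protocol Table 2-1 and SAP 1.2 give the filtration endpoint as "Estimated glomerular filtration rate (eGFR), as determined by the Chronic Kidney Disease Epidemiology Collaboration (CKD-EPI) equation", with no rate or slope.
- The protocol summary lists a tubular objective ("To determine the effect of nidufexor on renal tubular function as measured by free water clearance by the kidney") but no filtration objective among its secondary objectives. It does name eGFR under pharmacodynamic assessments and again under data analysis.
- Protocol 12.5.1 and SAP 2.6.1 specify the same analysis variable: "Log-transformed ratio to baseline for eGFR, free water clearance, HbA1c and fasting lipid profiles". Both apply the repeated-measures model used for UACR.
- In SAP 2.5.2.2 that model is set out as follows: "The model will include effects for log-transformed baseline, treatment, visit, treatment by visit interaction and visit by log-transformed baseline interaction". Protocol 12.4.2.2 lists the same effects. Treatment differences are reported at each visit.
- SAP 3 states: "No changes from protocol specified analysis were made".

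Parts of both documents are redacted, but protocol 12.5.1 and SAP 2.6.1 show no redaction mark.

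**The concern.** Someone who takes 4.1 and 8.3.3 literally will expect a rate per year and will find no rule that produces one. A rate needs a scale (percent or mL/min/1.73 m² per year), a method (Week 24 change, a slope including baseline, or a slope on treatment) and a clock (nominal or actual days). None of these is stated.

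The choices are not trivial. When eGFR shifts early and then drifts, different methods give different rates, and they can even reverse which of two patterns looks worse. Timing also appears to matter, because SAP 2.2 removes "EOS visit assessments when they were done earlier than day 135" and so keeps some visits well ahead of schedule. If these choices were made after unblinding, the reported rate would depend on them.

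**Working it through.** **The plan's own figure.** The documents give no power, SD or effect size for eGFR. The only such calculation is for UACR (protocol 12.8.1: 50 per arm, SD 0.6, true reduction 30%, estimated reduction of at least 25% required).
- SE = 0.6 × √(2/50) = 0.12.
- The one-sided 0.1 test needs an observed reduction of about 14.3%, so the 25% criterion is the binding one.
- Power = Φ((ln 0.75 − ln 0.70)/0.12) = Φ(0.575) = 0.717, against 72% stated.

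The figure reproduces, and the decision rule contains no eGFR term.

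**Does annualizing the planned contrast change the inference?** Let d be the Week 24 difference between arms in log ratio and t = 168/365.25 = 0.460 year. The annualized difference is d/t with standard error SE/t, so z = (d/t)/(SE/t) = d/SE. The p-value is the same, and the estimate and CI are multiplied by 365.25/168 = 2.174.

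**Scale.** Take an illustrative Week 24 nidufexor/placebo ratio of 0.97.
- Percent per year: 0.97^2.174 − 1 = −6.4%.
- At eGFR 30 (the entry floor in exclusion criterion 6): 30 × (−0.03) × 2.174 = −1.96 mL/min/1.73 m² per year.
- At eGFR 90 (assumed): 90 × (−0.03) × 2.174 = −5.87 per year.

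These are one result in different units.

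**Clock.** The End of Study visit is Day 169 ± 5, that is, Days 164 to 174, or 163 to 173 days after Day 1.
- Factors: 365.25/163 = 2.24 and 365.25/173 = 2.11, against 2.17 nominal.
- 163/168 = 0.970 and 173/168 = 1.030, a shift of about 3% either way.
- The extreme case is Day 135: 134 days, factor 365.25/134 = 2.73, and 134/168 = 0.798, so the nominal rule makes that patient's rate 20% smaller. Day 135 lies 29 days before the window opens (164 − 135).

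**Method.** Assume noise-free profiles from a baseline of 60 and eGFR on Days 1, 14, 29, 57, 85, 113, 141 and 169 (the eGFR row of Table 8-1 is not visible). Rates are in mL/min/1.73 m² per year.

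| Profile | Week 24 change, annualized | Slope with baseline | On-treatment slope |
|---|---|---|---|
| Drop of 3, then −2 per year | −8.5 | −5.1 | −2.0 |
| Rise of 2, then −8 per year | −3.7 | −5.9 | −8.0 |

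The visit-wise analysis avoids this ambiguity because it shows the shape directly. On the absolute scale:
- First profile: −3 − 2 × 28/365.25 = −3.15 at Day 29, and −3 − 2 × 168/365.25 = −3.92 at Day 169.
- Second profile: 2 − 8 × 28/365.25 = +1.39 at Day 29, and 2 − 8 × 168/365.25 = −1.68 at Day 169.

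**Precision of an added rate.** Assume 50 per arm, the visits above, complete follow-up, within-patient SD s = 4 to 8, slope SD b = 0 to 8 per year and between-patient SD T = 15 to 20.
- Slope: half-width = 1.96 × √[(2/50)(b² + s²/(Sxx/365.25²))], with Sxx = 26,363 day². This gives 3.53 (s = 4, b = 0) to 7.72 (s = 8, b = 8).
- Annualized baseline-adjusted Week 24 contrast: half-width = 1.96 × √[(2/50)(s² + T² + b²t² − T⁴/(T² + s²))]/t. This gives 4.74 (s = 4, b = 0, T = 15) to 9.82 (s = 8, b = 8, T = 20).

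On these assumptions, most half-widths are as large as or larger than the illustrative effects of 1.96 to 5.87 per year.

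**The case for a change.** The best argument for a change is that two protocol sections name a secondary endpoint that the visible plan never computes, and that tidying this would cost only a few words. The method table also shows that a rate chosen after the fact could tell different stories. Both points stand as far as they go. The inconsistency is there, and redaction is a weak defence because the eGFR analysis sections are visible in full.

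What does not stand is the step to a defect in the analysis.
- The harm requires a rate to be reported, and no visible analysis section calls for one.
- The Day 135 rule is not the only limit on End of Study data. SAP 2.2 also removes assessments more than 10 days from the last dose, and its list is open-ended and partly redacted. SAP 4.1 removes from Week 24 patients below 80% compliance and those who took study drug a month too long. The 20% timing effect is one extreme patient, and the documents do not say how many such patients there would be.
- SAP 3 is not contradicted on eGFR, since SAP 2.6.1 uses the analysis variable of protocol 12.5.1. The mismatch is internal to the protocol.
- Asking for either a random-slope model or a rescaled contrast leaves open the same choices of scale, method and clock.

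**Conclusion.** This is a wording slip, and no change to the plan follows. An analyst working from protocol 12.5.1 and SAP 2.6.1 has a complete, prespecified eGFR analysis: log ratio to baseline, baseline-adjusted, compared between arms at each visit. Its Week 24 contrast already measures the difference in decline over the treatment period, which is what 4.2 asks for, and multiplying by 2.17 adds no information. Correcting 4.1 and 8.3.3 would alter no result. A fitted slope would add an estimate with a half-width of about 3.5 to 7.7 per year in a secondary, non-confirmatory comparison that plays no part in the Go decision.

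The algebra on rescaling and the 3% timing figure rest only on the documents. The profiles and CI widths rest on assumed SDs, an assumed baseline and assumed eGFR visit days. A rate analysis could sit in redacted text, but the conclusion does not depend on that. It would differ if the sponsor reported an annualized rate as a formal result with no rule fixed beforehand, and nothing visible plans this.
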